#### Table 3Endpoint Specific Analysis Sets

$\Delta$ Leeds Enthesitis Index ( $\Delta$ LEI)	Include subjects with baseline LEI > 0	Baseline LEI = 0 means absence of enthesitis as measured by LEI. Enthesitis is not an enrollment criterion so it is expected that only a subset of the subjects will have enthesitis at baseline.
Resolution of enthesitis (LEI = 0)	Include subjects with baseline LEI > 0	Baseline $LEI = 0$ means absence of enthesitis as measured by LEI. Enthesitis is not an enrollment criterion so it is expected that only a subset of the subjects will have enthesitis at baseline.
%∆ in PASI and PASI clinical sign component scores	Include subjects with baseline BSA $\ge 3\%$ and baseline PASI $\ge 0$	PASI is not assessed if baseline BSA < 3% per the study protocol; PASI = 0 means absence of psoriasis as measured by PASI.
%ΔBSA	Include subjects with baseline BSA > 0%	Percent change from baseline cannot be calculated if baseline $BSA = 0\%$ .
ΔΝΑΡSΙ	Include subjects with baseline NAPSI > 0	Baseline NAPSI=0 means absence of nail psoriasis. Nail psoriasis is not an enrollment criterion so it is expected that only a subset of the subjects will have nail psoriasis at baseline.

## 5. GENERAL METHODOLOGY AND CONVENTIONS

#### 5.1. Hypotheses and Decision Rules

This protocol is designed to establish the superiority of tofacitinib 5 mg BID to placebo for treatment of rheumatological signs and symptoms of active PsA in subjects who have had an inadequate response in PsA to at least one csDMARD.

The null hypothesis is that there is no difference between tofacitinib 5 mg BID and placebo, and the alternative hypothesis is that there is a difference between tofacitinib 5 mg BID and placebo.

Tofacitinib 5 mg BID will be considered superior to placebo with respect to ACR50 response rate at Month 3 if the difference between tofacitinib 5 mg BID and placebo is statistically significant at the 2-sided 5% level, i.e., 2-sided p-value  $\leq 0.05$ .

For endpoints other than the primary (ACR50 response rate at Month 3), this study is not statistically powered to test the difference between tofacitinib 5 mg BID and placebo. Thus, any reported confidence intervals (CIs) and p-values should only be considered nominal.

### 5.2. General Methods

As subjects randomized to treatment group of placebo  $\rightarrow$  tofacitinib 5 mg BID (where  $\rightarrow$  means switching to) will advance from placebo to open-label treatment of tofacitinib 5 mg BID at Month 3, the treatment label used for reporting visits up to Month 3 will be "Placebo" and treatment label for reporting visits after Month 3 through Month 6 will be "Placebo  $\rightarrow$  Tofacitinib 5 mg BID".

For analyses through Month 3, the following treatment comparison will be made at each time point, where applicable:

• Tofacitinib 5 mg BID vs. Placebo.

For analyses after Month 3 through Month 6, the following treatment comparison will be made at each time point,

• Tofacitinib 5 mg BID vs. Placebo  $\rightarrow$  Tofacitinib 5 mg BID.

The primary efficacy comparison for the primary endpoint of ACR50 will be between tofacitinib 5 mg BID and placebo at Month 3.

#### **Descriptive Summaries:**

In general, the data for all continuous endpoints will be summarized by time point and treatment sequence in tables containing descriptive statistics (n, mean, standard deviation (s.d.), standard error (SE) of the mean, minimum, 1st, 2nd (median) and 3rd quartiles and maximum) for baseline and change or percent change from baseline for those endpoints measured at baseline. The data for all binary endpoints will be summarized by treatment group and by time point in tables showing descriptive statistics: N, n (i.e., number of responders), response rate (%), standard error of the response rate, and 95% confidence interval (CI) based on normal approximation. If  $\hat{p}$  is the estimated response rate, then the 95% CI is calculated as

$$\hat{p} \pm z_{0.975} \sqrt{\frac{\hat{p}(1-\hat{p})}{N}},$$

where  $z_{0.975}$  is the 97.5th percentile of the standard normal distribution and *N* is the number of subjects evaluable for the endpoint at the time point. If the lower bound is calculated to be negative, it will be set to 0%; if the upper bound is calculated to be larger than 100%, it will be set to 100%. In case when response rate is 0 or 100%, standard error will be reported as "NA" and the 95% CI will not be reported. The displays described above for continuous and response-type endpoints will only use available data with no imputation. Therefore, the calculation of response rates will use the number of evaluable subjects as denominators.

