#### 9.1. Sample Size Determination

The sample size and power analysis for the primary endpoint are based on the randomization of approximately 204 subjects in a 2:1 ratio. The sample size for this study is driven by the ACR50 response rate.

Assuming a placebo response rate of 9.5% and factoring in the number of subjects with primary endpoint missing due to COVID-19 (around 11 subjects as of 29 May 2020), a sample size of approximately 204 Chinese subjects (approximately 136 subjects in the tofacitinib treatment arm and 68 subjects in the placebo arm) randomized in a 2:1 ratio to tofacitinib and placebo arms will yield at least 90% power to detect a difference of 18.5% from placebo in ACR50 response rate, based on normal approximation (without continuity correction) at the 2-sided 5% significance level.

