#### **Reporting results:**

- Response rate without imputation: N, frequency and percentage of responders, SE of the response rate and 95% CI at Month 3 will be presented by treatment group.
- Response rate with imputation: N, frequency and percentage of responders, SE of the response rate at Month 3 will be presented by treatment group.
- Response rate difference with imputation: Difference between treatment groups, and corresponding SE, 95% CI and p-value at Month 3 will be presented.

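### The per-arm 95% confidence intervals in SAP 5.2 are Wald intervals, which at low response rates (mainly placebo) cover less than 95% and err mostly through an upper limit that is too low

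*SAP*

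**What the plan says.** SAP 5.2, Descriptive Summaries, specifies for every binary endpoint the response rate with its "standard error of the response rate, and 95% confidence interval (CI) based on normal approximation". The formula is the estimated rate plus or minus 1.96 times the square root of p(1−p)/N. Three rules go with it:

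- Truncation: "If the lower bound is calculated to be negative, it will be set to 0" percent, with the matching rule at 100%.
- Extremes: at an observed 0% or 100%, "the 95% CI will not be reported".
- Denominator: no imputation is used, and "the calculation of response rates will use the number of evaluable subjects as denominators".

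SAP 6.1.1.1 carries this into the primary endpoint: "Response rate without imputation: N, frequency and percentage of responders, SE of the response rate and 95% CI at Month 3". The rate with missing set to non-response gets no interval of its own: "Response rate with imputation: N, frequency and percentage of responders, SE of the response rate at Month 3". SAP 6.2.1 (secondary binary endpoints) and 6.4 (subgroups) follow the same pattern. No other interval for a single rate is specified. The small-count adjustment in 5.2.1.1 applies only to the difference between arms.

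The relevant planning figures are in Protocol 9.1: "Assuming a placebo response rate of 9.5" percent, with about 136 tofacitinib and 68 placebo subjects, and about 11 subjects missing the primary endpoint because of COVID-19.

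**The concern.** The Wald interval is unreliable when the expected number of responders is small. At 9.5% of 68, the plan expects about 6.5 placebo responders. When the observed count is low, the estimated standard error shrinks with it, so the interval is both too narrow and centred too low, and its upper limit tends to fall short of the truth. The reader of a responder table then sees a 95% label on an interval that covers less than that and understates how high the placebo rate could be. At zero responders the reader sees no interval, although zero out of 68 does bound the rate.

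**Working it through.** **Inputs.** Placebo rate 9.5%, arms of 136 and 68, difference 18.5 points and about 11 missing (Protocol 9.1). Other placebo rates from the global study in csDMARD inadequate responders (Protocol 1.2.2): ACR20 33.3% at Month 3 and 5.7% at Week 2. Assumption: if the 11 missing subjects split 2:1, placebo loses 11/3 ≈ 4, leaving about 64 evaluable. The documents do not give the split, so N = 60–68 is shown.

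**The plan's own figure.** The plan states no coverage. It does state that the sample "will yield at least 90% power to detect a difference of 18.5" points. With the unpooled standard error of SAP 5.2.1.1 and 28.0% against 9.5%, power is 94.2% with no missing data, 93.0% with 11 excluded 2:1, and 92.6% with 11 set to non-response 2:1. The statement reproduces, so the inputs are read correctly.

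**Method.** For each count x, compute L and U = x/N ∓ 1.96·√[(x/N)(1−x/N)/N], with L cut at 0. Then add the exact binomial probabilities of the counts where U lies below the true rate, where L lies above it, and where no interval is reported.

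**N = 68, true rate 9.5%.**
- x = 3: 0.0441 + 1.96 × 0.0249 = 0.0929, below 0.095. x = 4 gives 0.1147. The upper limit is too low for x = 1–3: 0.1028 − 0.0011 = 10.2%.
- x = 12 gives L = 0.0859 and x = 13 gives 0.0977. The lower limit is too high for x ≥ 13: 1.1%.
- Not reported: 0.905^68 = 0.1%.
- Coverage: 100 − 10.2 − 1.1 − 0.1 = 88.6%. Without the cut at zero it is identical.

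**N = 64, true rate 9.5%.** Three responders now give U = 0.0987, which covers. The upper limit is too low only for x = 1–2: 0.0503 − 0.0017 = 4.9%. The lower limit is too high 0.65% of the time, and coverage is 94.3%.

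**Across N at 9.5%.**

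| N | Wald coverage | Upper limit too low | Wilson coverage | Upper limit too low (Wilson) |
|---|---|---|---|---|
| 60–62 | 92.3–92.9% | 5.6–6.5% | 95.4–95.7% | 1.5–1.8% |
| 63–66 | 94.0–94.8% | 4.2–5.2% | 94.3–95.2% | 1.1–1.4% |
| 67–68 | 88.1–88.6% | 10.2–10.8% | 96.5–96.7% | 0.9–1.0% |
| Mean 60–68 | 92.5% | 6.4% | 95.4% | 1.3% |

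The jump at N = 67 arises because three responders stop covering 9.5% there. Over true rates of 8–12% and N = 60–68, mean Wald coverage among reported intervals is 91.9% (range 86.7–95.2%), and 89% of all misses are at the top.

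**Other rates.**
- 5.7%, N = 68: coverage about 90%, upper limit too low 7.6%.
- 2–4%, N = 68: the upper limit is never too low, because one responder already gives U = 4.3%. Reported intervals cover more than 99%.
- Omission at zero, N = 68: 0.98^68 = 25% at a true 2%; 0.99^68 = 50% at 1%.
- Illustrative subgroups at 9.5%: with 20 placebo subjects, 0.905^20 = 13.6% of tables show no interval; with 34, coverage is 84.3%.
- Placebo 33.3%, N = 68: 94.7%. Tofacitinib 28%: 95.3% at N = 136 and 93.5% at N = 129.

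**Examples.** 6/68: Wald 2.1–15.6%, Wilson 4.1–17.9%. 0/68: the SAP reports nothing; Wilson gives 0 to z²/(N + z²) = 3.84/71.84 = 5.3%.

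**The case against.** The case for leaving this alone has real force. The intervals sit under a descriptive heading, no decision rests on them, and SAP 6.4 disclaims inference within subgroups. N and the number of responders are always shown, so a reader can compute a better interval. With about 64 evaluable placebo subjects, total coverage at 9.5% is 94.3%; quoting 88.6% alone would pick the low point of a function that oscillates with N. All of that stands and is why the priority is low. It does not remove the one-sided error: at N = 64 the upper limit still misses about twice as often as it should. Nor does SAP 5.1 settle it, since its statement that intervals are only nominal concerns endpoints other than the primary, rests on lack of power, and does not restore coverage.

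A reader might infer more than the documents support:

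- *That the intervals flatter the treatment contrast.* The difference, its interval and its p-value come from SAP 5.2.1.1 on imputed data and do not use the per-arm limits. Below 50%, the Wald interval sits lower than Wilson in both arms.
- *That every responder table is affected.* The formula is used in all of them, but coverage is close to nominal near 28–33%.
- *That truncation or omission at zero is the cause.* Truncation leaves coverage unchanged, and omission has probability 0.1% at 9.5% with N = 68.
- *That the missing interval on the imputed rate is an error.* N, count, percentage and standard error are given, and the imputed difference has its own interval. This is a preference in presentation.

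**Conclusion.** The specification is wrong as written for low-rate cells: the 95% label does not hold near the planned placebo rate. The shortfall in coverage averages 2.5 points at 9.5% over N = 60–68 (from 0.2 points at N = 66 to 6.9 at N = 67), and the upper limit is too low 4.2–10.8% of the time against 2.5%. The amount of under-coverage depends on the evaluable placebo N, which the documents do not fix. The excess of misses at the top is present at every N from 60 to 68 at 9.5%, though not at true rates of 4% or less. The consequence is limited to the reported precision of low placebo rates. The primary test, the interval for the difference and the trial's conclusion are unaffected. Optional priority.

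**What to change.** In SAP 5.2, replace the per-arm formula with the Wilson score interval, [p + z²/2N ± z·√(p(1−p)/N + z²/4N²)] / (1 + z²/N). Report it at 0% and 100% as well. Delete the truncation rule, which is then unnecessary because the Wilson limits stay within 0–100%. Wilson is not perfect: at 9.5% and N = 60–68 its lower limit is too high 2.3–4.6% of the time, and at N = 63–66 the gain is in the upper limit rather than in total coverage. If a guaranteed minimum of 95% is preferred, Clopper-Pearson gives it at the price of wider limits (98.0% at N = 68 and 9.5%; 3.3–18.2% for 6/68).

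Adding the same interval to the imputed rates in SAP 6.1.1.1, 6.2.1 and 6.4 is optional. The cost is one formula in the SAP and one option in the program. Design, data collection, alpha and the primary analysis do not change.

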## 5.2.1. Analyses for Binary Data

#### 5.2.1.1. Normal Approximation

The normal approximation for the difference in binomial proportions (such as ACR50 response rate) can be used to test the superiority of tofacitinib 5 mg BID to placebo at postbaseline timepoints. The normal approximation to the test statistic for the difference in binomial random variables is calculated as

$$Z = \frac{\hat{p}_t - \hat{p}_c}{\sqrt{\frac{\hat{p}_t (1 - \hat{p}_t)}{N_t} + \frac{\hat{p}_c (1 - \hat{p}_c)}{N_c}}},$$

where  $\hat{p}$  refers to the relative frequency, N to the number of observations, the subscript c refers to the comparator group (e.g., placebo group) and the subscript t refers to the test group (e.g., tofacitinib 5 mg BID group) so that test statistics and p-values can be calculated for the contrast comparing the two treatment groups.

Two-sided 95% confidence intervals will be formed by

$$\hat{p}_t - \hat{p}_c \pm z_{0.975} \sqrt{\frac{\hat{p}_t (1 - \hat{p}_t)}{N_t} + \frac{\hat{p}_c (1 - \hat{p}_c)}{N_c}}$$

Two-sided p-value for the test of the 0 difference between tofacitinib 5 mg BID and placebo groups will be calculated as

$$p = 2(1 - \Phi(|Z|)),$$

where  $\Phi(\cdot)$  is the Gaussian cumulative distribution function.

If there is no (i.e., 0) response or 100% response in any one of the two treatment groups for the comparison, e.g., tofacitinib 5 mg BID vs. placebo, when calculating the proportions above, 0.5 will be added to the number of responses (i.e., numerator) and 1 will be added to the denominator in each treatment corresponding to the pair of comparison for calculating the treatment difference, standard error (i.e.,  $\sqrt{var(\hat{p}_t - \hat{p}_c)})$ , 95% CI and 2-sided p-value (Agresti, 2002). Estimated response rates and standard errors will be reported without adjustment for both groups. (Note that this adjusted method also applies to the case where the response rate is 0% in one treatment group and 100% in the other.)

When response rate of 0% is observed in both treatments or 100% in both treatments in comparison, no formal comparison will be performed. Estimated response rate of 0% or 100% will be reported as observed. Standard error will be reported as NA.

The final results will be expressed in percentages, i.e., (proportions  $\times 100$ )%.

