## 9.2. Efficacy Analysis

## 9.2.1. Analysis of Primary Endpoint of ACR50 Response Rate

The normal approximation to the difference in binomial proportions will be used to test the difference between tofacitinib 5 mg BID and placebo and to generate 95% confidence interval for the difference in response rates.

Missing values for any reason, eg, due to a subject dropping from the study or due to the impact of COVID-19 pandemic will be handled by setting the ACR50 value to nonresponsive. The SAP will also specify additional analyses to assess the sensitivity of the primary analysis to departures from the assumed missing data mechanism.

The analysis will include all randomized subjects who receive at least 1 dose of study drug.

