#### 9.2.2. Analysis of Secondary Endpoints

Binary endpoints will be analyzed similarly as for the primary analysis of ACR50.

The  $\Delta$ HAQ-DI will be analyzed using a repeated measure model that includes the fixed effects of treatment, visit (Week 2, Months 1, 2, 3, 4 and 6), treatment by visit interaction, and baseline value, and an unstructured variance covariance matrix for within-subject correlation (an alternative variance covariance matrix will be used if the model does not converge under the unstructured variance covariance matrix). Other continuous endpoints will be analyzed similarly.

Details of the analysis methods for all the endpoints will be enumerated in the SAP.

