6.1.1.1. Primary Analysis

Endpoint: ACR50 response rate at Month 3

- Analysis time points: Month 3
- Analysis population: FAS

- Method of imputation for missing data: MR=NR (specified in Section 5.3)
- Analysis methodology: The normal approximation to the difference in binomial proportions (specified in Section 5.2.1.1) will be used to test the difference between tofacitinib 5 mg BID and placebo and to generate 95% CI and p-value for the difference in response rates.

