#### **Figures:**

 $\circ$  Line graph of ACR50 response rate (using imputed data) with  $\pm$  SE will be plotted over time for both treatment sequences.

Note that ACR50 response rate at other timepoints will be analyzed by the same approach.

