#### 6.1.1.2. Supportive Analyses

Supportive Analysis 1: The analysis of ACR50 response rate at Month 3 described in Section 6.1.1.1 will also be conducted on the PP analysis set since the FAS may include instances of non-compliance which may diminish the potential efficacy of tofacitinib. This will serve as a supportive analysis of the primary endpoint.

Endpoint: ACR50 response rate at Month 3

- Analysis time points: Month 3
- Analysis population: PP analysis set
- Method of imputation for missing data: MR=NR (specified in Section 5.3)
- Analysis methodology: Normal approximation (specified in Section 5.2.1.1)

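### The unpooled Wald z-test for ACR50 at Month 3 does not hold the stated two-sided 5% level: its exact error is 6.2% at 136/68 and the planned 9.5% rate

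*SAP*

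**What the plan says.** SAP 5.2.1.1 sets out the method: "The normal approximation for the difference in binomial proportions (such as ACR50 response rate) can be used to test the superiority of tofacitinib". Its formula divides the difference in observed rates by a standard error built from each arm's own observed rate (the unpooled, or Wald, form) and takes the p-value from the normal distribution. If one arm has 0% or 100% response, half a response is added to the numerator and one subject to the denominator in both arms.

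SAP 6.1.1.1 names this as the primary analysis on the FAS, with missing response counted as non-response (MR=NR). It "will be used to test the difference between tofacitinib 5 mg BID and placebo and to generate 95% CI and p-value". SAP 5.1 sets the decision rule: superiority is claimed if the difference is "statistically significant at the 2-sided 5% level". For every other endpoint, "any reported confidence intervals (CIs) and p-values should only be considered nominal".

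Protocol 9.2.1 is less specific: "The normal approximation to the difference in binomial proportions will be used to test the difference between tofacitinib 5 mg BID and placebo". It does not say which variance is used. Protocol 9.1 plans 136 and 68 subjects, a 9.5% placebo rate, an 18.5-point difference and at least 90% power, allowing for about 11 subjects with the endpoint missing because of COVID-19.

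**The concern.** If the two true rates are equal, the 68-subject placebo arm carries two thirds of the variance, because (1/68)/(1/68 + 1/136) = 2/3. The unpooled formula estimates that share from the observed placebo rate. When placebo response is low by chance, the difference looks large and its estimated standard error shrinks at the same time. The errors therefore pile up on the side that favours tofacitinib.

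This test carries the trial's only confirmatory claim. If its true level is above 5%, a borderline result could be declared significant when a test that holds the level would not support it.

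No planned analysis would show that this had happened:

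- The per-protocol analysis, which "will also be conducted on the PP analysis set", reuses the same formula, as do the COVID-19 analysis (SAP 6.7.1) and the subgroup analyses (SAP 6.4).
- The tipping-point analysis applies the formula to each imputed data set.
- The repeated-measures logit model (GMMRM) gives a Month 3 odds ratio and p-value, but without MR=NR. A disagreement could come from the missing-data handling as easily as from the test.

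**Working it through.** **Inputs.** Arm sizes 136/68, placebo rate 9.5%, difference 18.5 points (28.0% vs 9.5%) and 11 missing are from Protocol 9.1. The statistic and its zero-cell rule are from SAP 5.2.1.1, and the two-sided 5% level is from SAP 5.1. A second null rate of 14.5% is the placebo rate of study A3921125 in Protocol 1.2.2, a population with inadequate response to TNF inhibitors. Assumption: the 11 missing subjects are spread 2:1.

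**Step 1: the plan's power figure.**

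- Unpooled SE = √(0.28×0.72/136 + 0.095×0.905/68) = 0.0524. Power = Φ(0.185/0.0524 − 1.96) = 94.2%.
- With 11 of 204 as non-responders, both rates are multiplied by 193/204, giving 26.5% vs 9.0%. Power is then 92.6%.
- With the pooled null variance, the same two figures are 89.2% and 86.7%.

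The claim of at least 90% therefore reproduces, but only with the unpooled test.

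**Step 2: exact type I error.** For a common rate p, sum the binomial probabilities of all outcome tables (x, y) with |Z| ≥ 1.96, where

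Z = (x/136 − y/68) / √(p̂t(1−p̂t)/136 + p̂c(1−p̂c)/68),

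with the 0.5/1 rule, and no test if both arms are 0% or both are 100%. Results at 136/68:

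| Common rate | Favouring tofacitinib | Favouring placebo | Two-sided |
|---|---|---|---|
| 3% | 2.05% | 0.93% | 2.98% |
| 5% | 4.64% | 1.23% | 5.87% |
| 7% | 4.85% | 1.46% | 6.31% |
| 9.5% | 4.58% | 1.64% | 6.22% |
| 14.5% | 3.93% | 1.90% | 5.83% |
| 28% | 3.16% | 2.27% | 5.43% |

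The zero-cell rule hardly matters: at 9.5% the error is 6.22% with it and 6.23% without it.

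**Step 3: sensitivity to arm size.** The grid is 130–142 vs 64–72, which is 117 pairs:

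| Common rate | Two-sided error | Pairs above 5% |
|---|---|---|
| 3% | 2.47–4.32% | 0 |
| 4% | 3.84–5.56% | 32 |
| 5% | 4.82–6.16% | 111 |
| 9.0% (9.5% × 193/204) | 5.23–6.26% | 117 |
| 9.5% | 5.23–6.24% (mean 5.79%) | 117 |
| 14.5% | 5.30–5.94% | 117 |
| 28% | 5.25–5.59% | 117 |

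All 117 pairs exceed 5% at every rate tried from 5.3% to 30%.

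**Step 4: alternatives at 9.5%, same grid.** The Miettinen–Nurminen score test uses the pooled null variance times N/(N−1). It gives 4.64–5.22% (mean 4.87%, 33 of 117 pairs above 5%). The pooled z-test gives 4.64–5.40% (mean 4.92%, 45 of 117 above 5%).

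**Step 5: a borderline case, 20/136 vs 4/68.** The rates are 14.7% and 5.9%, a difference of 8.8 points.

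- Unpooled: SE = √(0.1471×0.8529/136 + 0.0588×0.9412/68) = 0.0417, Z = 2.12, p = 0.034, CI 0.7 to 17.0 points.
- Pooled: rate 24/204 = 0.1176, SE = √(0.1176×0.8824×(1/136 + 1/68)) = 0.0479, Z = 1.84, p = 0.065.
- Score: p = 0.066, CI −0.7 to 16.9 points.

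Likewise 25 vs 6 gives p = 0.046 (unpooled) and 0.074 (score). At 38 vs 6, about the planned rates, p = 0.0002 and 0.0018.

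**Step 6: how often the verdict differs.** At 136/68, tofacitinib would win by the unpooled test but not by the score test in 2.56% of trials under the 9.5% null. The figure is 3.47% at the design effect with 11 non-responders. The reverse essentially never happens.

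**Step 7: exact power at 136/68.**

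| Rates | Unpooled | Pooled | Score |
|---|---|---|---|
| 28.0% vs 9.5% | 92.6% | 89.7% | 89.7% |
| 26.5% vs 9.0% (11 non-responders) | 90.9% | 87.5% | 87.5% |

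**The case against.** The test is standard, fully pre-specified and consistent between the two documents. Every alternative is also approximate: the score test itself passes 5% in 33 of the 117 pairs. The protocol's power figure reproduces only with the unpooled form, so that form may well be what the protocol meant. The excess is small, matters only near the boundary, and disappears at very low response rates. The documents call the arm sizes approximate and set no limits, so the grid is the reviewer's choice; with ±6 in both arms the maximum rises to 6.4%. Replacing the test takes power below the level that Amendment 4 enlarged the trial to protect. It also leaves ACR50 tested differently at Month 3 from other visits and from the tipping-point analysis. On this view a sensitivity analysis is enough.

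Much of this stands. The excess is modest, the power cost is real, and the split in methods is a genuine inconvenience. The GMMRM is a partial cross-check, though not a clean one. None of it removes the excess: at the plan's own sizes and rate the error is 6.2%, not 5%, and the score test's largest error on the grid at that rate is 5.2%. Part of the unpooled test's power advantage comes from the same inflated tail.

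**Conclusion.** The concern holds. At 136/68 and a 9.5% common rate the primary test's exact two-sided error is 6.22%. The tail that supports a superiority claim is 4.58%, against the 2.5% that a two-sided 5% test implies. Near plan the excess over 5% is 0.2 to 1.2 points.

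This rests on true null rates of about 5.3% or more and on realised arm sizes of 130–142 and 64–72. At a 5% rate 6 of the 117 pairs no longer exceed 5%, and at 3% none do. A result near the design effect would not change verdict. The power statement in Protocol 9.1 is correct for the unpooled test and needs restating only if the test changes. This should be fixed before unblinding.

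**What to change.** **Preferred.** Test ACR50 at Month 3 with the Miettinen–Nurminen score test and report its score interval. Keep the estimand, the FAS and MR=NR. The SAP already uses Miettinen–Nurminen methods for Tier-2 adverse events (SAP 5.2.3).

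1. SAP 6.1.1.1 and Protocol 9.2.1, new text: *The difference in ACR50 response rates at Month 3 will be tested with the Miettinen–Nurminen score test (2-sided 5%), and its 95% CI will be the corresponding score interval.*
2. SAP 5.2.1.1, add: *This formula and its 0.5/1 rule do not apply to ACR50 at Month 3, except within the imputed data sets of the tipping-point analysis.*
3. Use the score method in Supportive Analysis 1 (SAP 6.1.1.2), SAP 6.7.1 and SAP 6.4 (CI only), and change the primary, per-protocol, COVID-19 and subset rows of Appendix 1.
4. Leave ACR50 at other visits and the binary secondary endpoints on the normal approximation, as nominal analyses. Delete the SAP 6.1.1.1 note "Note that ACR50 response rate at other timepoints will be analyzed by the same approach", since SAP 6.2.1 already covers those visits. In Protocol 9.2.2 replace "Binary endpoints will be analyzed similarly as for the primary analysis of ACR50" with: *Binary secondary endpoints will be analyzed with the normal approximation to the difference in binomial proportions; p-values are nominal.*
5. Keep the normal approximation in the tipping-point analysis, because Rubin's rules need an estimate and a standard error. Delete the closing sentence of Appendix 4 Step 5, which says the method matches the primary analysis.
6. Restate power in Protocol 9.1 and the Protocol Summary as about 87.5% with 11 subjects counted as non-responders.

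**Cost.** SAP wording and a protocol amendment, since Protocol 9 requires one for a major change to the primary analysis. No new data are needed. Exact power falls from 90.9% to 87.5%; reaching 90% would take about 219 subjects instead of 204. The score test is close to 5% but not exact: at a 5% null rate it reaches 5.6% (12 of 117 pairs above 5%), and at 9.5% its tail favouring placebo reaches 3.1%.

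**Smaller change.** Use a pooled-variance z-test in SAP 5.2.1.1. This fits the present wording of Protocol 9.2.1 and 9.2.2 and of Appendix 1, but has the same power cost, and Appendix 4 needs a note on the standard error. The unpooled CI could then contradict the test: at 20 vs 4, p = 0.065 with a CI of 0.7 to 17.0 points.

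**Minimum.** Keep the Wald test and pre-specify the score test as a sensitivity analysis. This needs only SAP wording and costs no power. It exposes a borderline result but does not restore the 5% level.
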